Pain after Cesarean section- A Danish multicenter cohort study.

Document date: 11.8.23

NCT ID: Not yet assigned

Background

Worldwide, more than 20 million children are born by cesarean section each year (World Health Organization 2021), making it one of the most commonly performed surgical procedures. Postoperative pain is typically moderate to severe in intensity (Sun and Pan 2019) and inadequate pain relief significantly affects the new mother's ability to mobilize and care for herself and her baby (Ciechanowicz et al. 2019). Pain may also impact recovery and negatively affect the early bonding between mother and child, as well as the establishment of breastfeeding (Roofthoof et al. 2021). Furthermore, there might be a correlation between inadequately treated acute pain and the development of chronic pain after cesarean section (Nikolajsen et al. 2004; Yimer and Woldie 2019). All these factors emphasize the necessity of effective pain management following cesarean section.

Only a few studies describe pain following cesarean section in a Danish population. Nikolajsen et al. (Nikolajsen et al. 2004) investigated the prevalence of chronic pain among 220 patients interviewed one year after cesarean section. A total of 46.8% recall to have experienced severe pain in the period shortly after the cesarean section. In a Danish randomized placebo-controlled trial involving 72 patients (Hansen et al. 2019) reported pain scores in patients allocated to either a Transmuscular Quadratus Lumborum block (TQL) or placebo TQL following a cesarean section. Both groups had access to intravenous morphine via patient-controlled analgesia. The patients scored their pain on a numeric rating scale (NRS), ranging from 0 to 10, where 0 is no pain and 10 is the most severe pain imaginable. After 6 hours, the TQL block group had an NRS (0-10) of 4 during movement, while the placebo group had an NRS of 5. At 12, 18 and 24 hours, both groups had similar NRS scores of 5, 4, and 3, respectively. The average 24-hour oral morphine equivalent consumption was 65 mg for the TQL block group, compared to 94 mg for the group given placebo.

That dosage is significantly higher than recently described in a Danish uni-center quality study of 100 patients ([name] 2023). Among these patients, 85 received the standard postoperative pain management for cesarean section, which aligns with the pain treatment protocols employed in most hospitals across the country: A fixed dose of paracetamol and NSAID, supplemented with oral morphine; nerve blocks or intrathecal morphine are not given routinely. The median 24-hour oral morphine equivalent dose given to the patients by request to the nurses was 30 mg (IQR: 20-50). The relatively lower opioid dose may suggest an existing underestimation and suboptimal treatment of the patients' pain. At 6, 12, 18 and 24 hours after the cesarean section the reported average NRS (0-10) pain scores during movement were 7,

6, 6, and 5 respectively, corresponding to moderate or severe pain, and further supports the possibility of underestimation and undertreatment of post-cesarean pain.

In a Danish multicenter survey conducted in 2020 to 2021 (Lindelof 2022), 861 cesarean section patients were asked 24-48 hours after surgery how much they agreed on having “experienced severe pain after the cesarean section” In this assessment, 45% scored ≥ 8 (NRS 0-10).

Overall, there is strong indications that currently a substantial number of women in Denmark experience severe pain in the first days after their cesarean section. To address this, we have established an obstetric-anesthesiologic research cluster as part of the national perioperative research network, CEPRA (Nørskov et al. 2023) with an aim to optimize pain treatment for the approximately 12,700 Danish patients who undergo cesarean section every year.

Objective

This study aims to map postoperative pain in Danish patients undergoing elective cesarean section. Specifically postoperative pain levels, impact on physical function, side effects from pain medication, and treatment approaches in the postoperative period.

Furthermore, we aim to test the feasibility of repeated SMS-based questionnaires sent to the patients in the postoperative period. Based on response rates and frequency of outcomes, data from this observational study will also be used to inform a randomized controlled multicenter trial aiming to test better postoperative pain interventions for cesarean section patients.

Method

Study design

Prospective Danish multicenter cohort study based on patient-reported outcomes (SMS-based questionnaires) and clinical data from electronic health records.

Inclusion criteria

Patients who undergo planned cesarean section under spinal anesthesia.

Patients who speak and read Danish and can provide informed consent to participate.

Patients who have a smartphone that can receive an SMS with a link to a questionnaire that can be accessed on an online website on the phone.

Exclusion criteria

Age < 18 years

Number of participants

Minimum 400 patients, included from minimum 9 centers representing all 5 regions in Denmark.

Outcomes

Outcomes have been selected to align with the outcomes in a subsequent randomized controlled multicenter trial, where we will investigate whether the addition of intrathecal morphine provides better postoperative pain control. Therefore, opioid side effects are given high priority in the outcome measures.

The following abbreviations are used in the section outcome measures:

Time intervals are specified as the time difference from the administration of the spinal anesthesia (t0), and outcomes are assessed either through patient questionnaires (P) or by reviewing medical records (J).

Outcome measures

Maternal outcomes

Primary outcomes

- Level of pain during the activity from lying to a seated position, after 24 hours. NRS 0-10 (P)
- Morphine associated adverse events within 24 hours after CS, assessed as a binary outcome including nausea, vomiting, dizziness, itching, or urine-retention (P). Vomiting and urine-retention, will be reported as yes/no. Nausea, dizziness and itching will be assessed as “none”, “little”, “moderate”, or “severe”, with patients reporting “moderate” or “severe” categorised as having a positive outcome.

Secondary outcomes

- Opioid consumption within the first 24 hours after caesarean section (oral morphine equivalents, mg) (J)
- Insufficient spinal anesthesia related adverse events during the caesarean section, as binary composite outcome of the proportion of patients in need of conversion to general anesthesia, intraoperative opioids, sevoflurane, or nitrous oxide for intraoperative pain, or repeated neuraxial procedure (spinal or epidural placement following failed spinal). (J)
- Level of pain during the activity from a lying to a seated position, after 6, 12, 18 hours. NRS 0-10 (P)
- The ability to mobilize independently at 24 hours after surgery. Yes/No (P)
- The ability to nurse infant independently at 24 hours after surgery. Yes/No (P)

Exploratory outcomes

- Level of pain at rest 6, 12, 18, 24, 48 hours, 7 days, and 30 days after surgery. NRS 0-10 (P)
- Use of analgesic medication (Paracetamol (PCM), Non-Steroidal Anti-Inflammatory Drug (NSAID) and opioid) 6, 12, 18, 24, 48 hours, 7 days, and 30 days postoperatively. Yes/No. (P)
- Level of pain during the activity from a lying to a seated position after 48 hours, 7 days and 30 days. NRS 0-10 (P)
- Localization of pain: Abdomen, shoulder, head, back, other. 6, 12, 18, 24, 48 hours. (P)

- Need for unplanned "rescue" ultrasound-guided truncal nerve block or epidural within 24 hours. Yes/No (J)
- Maternal satisfaction with pain-treatment during the first 24 hours. Assessed after 24 hours. Likert scale of 0-4. Very dissatisfied, dissatisfied, neither satisfied nor dissatisfied, satisfied, very satisfied. (P)
- Pain related self-efficacy and self-empowerment after surgery: The feeling of being in control during the first 24 hours, assessed after 24 hours, Likert scale (0-4). (P)
- Composite outcome of rare maternal adverse events (J):
 - Clinically significant maternal respiratory depression within 24 hours defined as the need for airway intervention; oxygen therapy >3 L/min; administration of an opioid antagonist to counteract depressed respiration; or an intervention beyond verbal stimulus to rouse the patient from sedation reported the first 24h after surgery *or*
 - Maternal hospital readmission within 7 days, *or*
 - Maternal re-attendance or unplanned out-patient visit within 7 days.
- The ability to handle own personal hygiene 24 hours after surgery. Yes/No (P)
- Itching after 6, 12, 18, 48 hours, 4-point scale: None, mild, moderate, severe (P)
- Dizziness after 6, 12, 18, 48 hours, 7 days, and 30 days, 4-point scale: None, mild, moderate, severe (P)
- Nausea after 6, 12, 18, 48 hours, 7 days, and 30 days, 4-point scale: None, mild, moderate, severe (P)
- The impact of pain on how often the patient has gotten out of bed in the last 6 hours. 6, 12, 18, 24, 48 hours. 4-point scale: None, a little, moderate, a lot (P).
- The impact of pain on how much the patient has breastfed or bottle-fed the infant in the last 6 hours? 6, 12, 18, 24, 48 hours. 4-point scale: None, a little, moderate, a lot (P).
- The impact of pain on the ability to resume regular daily activities. 7 and 30 days. 4-point scale: None, a little, moderate, a lot (P)
- Obstetric Quality of Recovery score using Obs-QoR-10 (Pervez Sultan et al. 2020; P Sultan et al. 2020)

How much have you been bothered by this problem in the past 24 hours?

1. Pain. 24 hours. None-worst imaginable 0-10. (P)
2. Nausea or vomiting. 24 hours. None-worst imaginable 0-10. (P)
3. Dizziness. 24 hours. None-worst imaginable 0-10. (P)
4. Shivering. 24 hours. None-worst imaginable 0-10. (P)
5. I have been comfortable. 24 hours. Not at all - all the time 0-10. (P)
6. I am able to mobilize independently. 24 hours. Not at all - all the time 0-10. (P)
7. I can hold my baby without assistance. 24 hours. Not at all - all the time 0-10. (P)
8. I can feed/nurse my baby without assistance. 24 hours. Not at all - all the time 0-10. (P)
9. I can look after my personal hygiene in the past 24 hours. 24 hours. Not at all - all the time 0-10. (P)
10. I feel in control in the past 24 hours. 24 hours. Not at all - all the time 0-10. (P)

- Global Health Score (Euroqol 2023) 24 hours. Worst-best imaginable health state 0-100 (for validation of Obs-QoR-10) (P)
- Response rates for questionnaires after 6,12,18,24,48 hours plus 7 and 30 days after the cesarean section.
- Response time for questionnaires after 6,12,18,24,48 hours plus 7 and 30 days after the cesarean section.

Neonatal outcomes

Primary outcome

- Need for neonatal admission within 24 hours (yes/no). (J)

Secondary outcomes

- Infants in need of respiratory support within 48 hours (continuous positive airway pressure treatment, positive pressure ventilation, HNF (nasal high flow), intubation or oxygen therapy). Yes/No and time (J)
- Proportion with established breastfeeding at 30 days following delivery, if intended. (P)

Exploratory outcomes

- Apgar score at 5 minutes. (J)
- Apgar score at 10 minutes. (J)
- Proportion of infants with Apgar <7 at 5 minutes. (J)
- Readmission within 24 hours after discharge. Yes/No.
- Readmission within 7 days after discharge. Yes/No.

Development and validation of questions:

The questions were developed with inspiration from international consensus regarding obstetric recovery, including the incorporation of the Obs-QoR-10 score (Pervez Sultan et al. 2020; P Sultan et al. 2020) and the use of NRS scores for pain assessment (Eisenach et al. 2008; Hansen et al. 2019). Additionally, we have drawn on experience and knowledge gained from the pilot study by [name] et al. ([name] 2023) preceding this national study, which involved the participation of 100 patients. Patients, maternity staff, anesthetists, and obstetricians was consulted to determine the key areas of focus during the first postoperative days after a cesarean section. The questions were developed and validated by using standardized methods for designing and conducting surveys (Eysenbach 2004; Burns et al. 2008). Subsequently, the questionnaires were created in the database: Research Electronic Datacapture (REDCap) (“RedCap” n.d.)

Data collection

All data is entered directly into the closed and secure system, REDCap (Harris et al. 2009), which is approved by all the regions in Denmark. Questionnaires are sent to the patient after 6, 12, 18, 24, and 48 hours, as well as 7 and 30 days after spinal anesthesia for cesarean section (t0). The questionnaires are delivered to

the patient's smartphone as an SMS with a link to a questionnaire in REDCap. Data from journal entries are also entered into REDCap. At all hospitals, there is a data manager who has access to REDCap and can retrieve data for the patients included in the project. The primary investigator holds the overall responsibility.

Ethics and approvals

This study complies with the Helsinki declaration. The protocol will be made available on the website clinicaltrials.gov prior to inclusion of patients. Participation is completely voluntary, and consent can be withdrawn at all times.

Data Protection Authority

Approval for data collection, handling and storage has been granted by the data protection authority for the Capital Region (Region Hovedstaden) with case number P-2023-90. This includes approved data agreements between the Danish Regions, with a designated data manager from each participating hospital. (See Appendix 1)

Research Ethics Committee

The Research Ethics Committee (VEK) and the regional research ethics committee for the Capital Region of Denmark (Region Hovedstaden) have been presented with the project description and protocol and have waived the need approval due to Danish legislation. Case number F-23004686. (See Appendix 1)

Informed consent

Verbal informed consent is obtained during the inclusion process with each patient. The patient must consent to receive questionnaires on the mobile phone and to the data manager accessing the medical records related to the cesarean section for the patient and the baby. The patient is informed that participation is voluntary and that their data will be securely stored. Written description of the consent is electronically sent to the patient, including a description of how to withdraw consent. This is approved by the data protection authority for the Capital Region of Denmark (Region Hovedstaden) with case number P-2023-90

Data Processing and statistics

All data will be handled in the secure REDCap database. Descriptive statistics will be used to analyze data. Continuous data will be summarized as median (interquartile range) or mean if the data is normally distributed. We plan to do a subgroup analysis on the groups where intrathecal morphine or TQL block has been administered. And categorical data as frequency (percentage). We will try to minimize missing data as much as possible, by sending questionnaires directly to the participants mobile phones. Number of missing data will be accounted for when describing data. Sample size is determined by convenience. The study is designed to be as large as possible, as all hospitals in Denmark, handling elective cesarean sections, will be invited to participate. Larger sites (>300 elective CS per year) commits to include 50 patients, medium scale sites (200-300 elective CS per year) commit to include 40 patients, and smaller sites (<200 elective CS per year) commits to include 30 patients.

Collaboration Agreement

A collaboration agreement has been established between project leaders and site coordinators, outlining mutual obligations and rules for data usage.

Inclusion Period

01.09.2023-31.12.2024, 1-6 months depending on the rate of inclusion at different sites.

Participating Departments

Maternity units from all 5 Danish regions. The following hospitals have agreed to participate:

Capital Region of Denmark (Region Hovedstaden): Hilleroed, Herlev, Hvidovre, Rigshospitalet

Region Zealand (Region Sjælland): Roskilde

Region of Southern Denmark (Region Syd): Kolding, Odense

Central Denmark Region (Region Midt): Aarhus

North Denmark Region (Region Nord): Aalborg

The study is open for all Danish hospitals, where elective cesarean sections are performed. If any additional hospitals should wish to participate in the study within the specified time period, they will be included.

Data to be collected from the patient's medical record

Patient characteristics

- Pre-pregnancy BMI
- Parity
- Indication for cesarean section: Maternal request/Previous cesarean section as the only indication/Breech presentation/Maternal indication/Obstetric indication/Fetal indication/Other indication.
- Previous number of cesarean sections: 0, 1, 2, 3, or ≥ 4
- Previous abdominal surgeries: Yes/No. If yes: Laparoscopic or laparotomy
- Chronic pain patient (receiving regular opioid or other pain treatment besides NSAIDs and PCM) within 0-2 months prior to cesarean section: Yes/No
- Inflammatory bowel disease (Crohn's disease or ulcerative colitis): Yes/No
- Pregnancy-related illness? No/Gestational hypertensive disorder (Preeclampsia including HELLP, Gestational hypertension)/Gestational diabetes, Other.

Anesthesia information

- Spinal anesthesia: Bupivacaine, sufentanil, fentanyl, morphine. Mg and ml.
- Was the patient given an epidural-spinal? Yes/No
- Was general anesthesia administered as the initial preference for the patient? Yes/No
- Was the spinal anesthesia converted to epidural? Yes/No
- Was the spinal anesthesia converted to general anesthesia? Yes/No
- Was the spinal repeated following a failed spinal? Yes/No
- Was it necessary to supplement the spinal anesthesia with opioids, nitrous oxide, or similar due to breakthrough pain during the operation? Yes/No
- Did the patient have an epidural when going to the maternity ward after the recovery period? Yes/No. If yes: When was the epidural discontinued? Date and Time.

Operation information

- Operation time (minutes)
- Intraoperative bleeding. ml.
- Has the uterus been exteriorized during the operation? Yes/No/The information was not found in the medical record.
- Postoperative bleeding within the first 48 hours requiring blood transfusion. Yes/No
- Reoperation within the first 30 days: Yes/No. If yes: Abdominal bleeding/Vaginal bleeding/Suspected retained tissue or endometritis/Infection at the incision site/other reason

Pain management

- Nerve blockade within the first 24 hours after the cesarean section: Yes/No; Time; Block type, dose, medication, reason.
- Placement of an epidural within the first 24 hours after the cesarean section: Yes/No; Time, reason

- Opioid consumption within 0-24 hours, mg oral morphine equivalents
- Opioid consumption within 25-48 hours, mg oral morphine equivalents
- Administration of dexamethasone within the first 24 hours after cesarean section: Yes/No. Dose.
- Administration of antihistamine as itch relief within the first 24 hours: Yes/No
- Administration of naloxone as itch relief within the first 24 hours: Yes/No

Maternal hospitalization

- Duration of total hospital lengths of stay after cesarean section (number of days)
- Maternal readmission or unplanned outpatient consultation within 7 days. Yes/No
- Occurrence of clinically significant maternal respiratory depression within 24 hours, defined as the need for airway intervention; oxygen therapy >3 L/min; administration of an opioid antagonist to counteract depressed respiration; or an intervention beyond verbal stimulus to rouse the patient from sedation. Yes/No
- Ogilvie's syndrome/ileus, that requires surgery or neostigmine within the first 7 days after cesarean section: Yes/No

Infant

- Apgar score at 5 minutes
- Apgar score at 10 minutes
- Neonatal hospitalization within 24 hours: Yes/No
- Neonatal readmission within 24 hours: Yes/No
- Neonatal readmission within 7 days: Yes/No
- Neonatal need for respiratory support within 48 hours (CPAP, PPV, HNF, intubation, or oxygen supplementation): Yes/No; Time of initiation; Duration (hours < 24 or number of days > 1)

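### Does timing the 24-hour opioid outcome from the spinal injection bring intrathecal, intra-operative or epidural opioid into the total?

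*Protocol*

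**What the plan says.** The Outcomes section times every outcome from one origin, whether it comes from questionnaires or from records: "Time intervals are specified as the time difference from the administration of the spinal anesthesia (t0"). The maternal secondary outcome is "Opioid consumption within the first 24 hours after caesarean section (oral morphine equivalents, mg) (J"), and the record item that feeds it, under Pain management, is "Opioid consumption within 0-24 hours, mg oral morphine equivalents". Neither names a route or an exclusion.

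The next secondary outcome, on insufficient spinal anesthesia, has among its components "intraoperative opioids, sevoflurane, or nitrous oxide for intraoperative pain". Under Anesthesia information the spinal drugs have their own dose field: "Spinal anesthesia: Bupivacaine, sufentanil, fentanyl, morphine. Mg and ml". Supplementation for breakthrough pain during surgery is recorded there only as Yes/No.

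An epidural still in place on transfer is recorded by "Did the patient have an epidural when going to the maternity ward after the recovery period? Yes/No" and, if present, its stop time. A new one is recorded under Pain management: "Placement of an epidural within the first 24 hours after the cesarean section: Yes/No; Time, reason". The adjacent nerve block item asks for more: "Nerve blockade within the first 24 hours after the cesarean section: Yes/No; Time; Block type, dose, medication, reason".

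**The concern.** A data manager who applies the clock literally would add any opioid given in theatre to the 24-hour total, and perhaps the opioid in the spinal as well. One who follows the grouping of the record items would leave both out. At least nine centers extract this outcome, so two careful people could reach different totals for the same patient.

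An intrathecal dose could be subtracted later from its own field. An intra-operative or epidural dose could not be separated using the listed items, because they ask for no amount.

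The stake looks larger for the planned intrathecal morphine subgroup and for the later trial that this study is meant to inform. If intrathecal morphine were counted, the same dose would both define the subgroup and add to its outcome.

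**Working it through.** The protocol states no figure that could be reproduced here. Its sample size is one of convenience and its analysis is descriptive. The check is therefore a comparison of texts, followed by a statement of scale.

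**1. Clock.** The response-rate outcomes time the questionnaires from the cesarean section, while Data collection times the same questionnaires from t0. The operation is thus used as shorthand for t0, and the origin is not in doubt. Even if it were, an assumed delay of 0.5 to 2 hours would move the window by only 0.5/24 = 2.1% to 2/24 = 8.3% of its length. What matters is which doses count.

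**2. Which doses count.**

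| Source of opioid | Where the protocol puts it | Position |
|---|---|---|
| Spinal injection | Anesthesia information, with dose | Given at t0 itself, so a boundary case; own field |
| Intra-operative | Separate secondary outcome; Yes/No under Anesthesia information | Inside the window by the clock, outside it by the grouping |
| Postoperative, by request | Pilot figure in Background; Pain management | Counted on either reading |
| Postoperative epidural | Yes/No with times or reason | Inside the window on either reading; no route restriction stated |

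The stated objective also concerns treatment in the postoperative period. Only the second row sets the two readings clearly against each other.

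**3. Scale in one affected patient.** The pilot study in Background gives a median of 30 mg (IQR 20-50) for opioid given on request. The protocol gives no dose for the disputed opioid, so these amounts are assumptions:

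- 3 mg: 3/30 = 10% of the median
- 10 mg: 10/30 = 33% of the median

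The IQR width is 50 - 20 = 30 mg, so the same amounts are 10% and 33% of that spread.

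**4. Scale in the cohort.** Data Processing and statistics plans a median with IQR unless the data are normally distributed. Adding at most *a* mg to some patients' totals raises the median by at most *a*. From 30 mg, the ceiling is 33 mg for *a* = 3 and 40 mg for *a* = 10. If only a share *p* of patients is affected, the new median also cannot exceed the old (50 + 100*p*)th percentile. The protocol does not give *p*, so no cohort effect can be stated.

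**5. Recovery.** Patients who had supplementation, conversion to general anesthesia or an epidural are flagged in the listed items. They can be identified and set aside. The supplementation flag also covers nitrous oxide, so it picks out somewhat more patients than those given opioid.

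**The case for a change.** The strongest argument for a change is that this concerns what sites write down, and a later analysis plan cannot recover amounts that were never recorded separately. The outcome's own wording does not close the question, because the protocol elsewhere uses the operation as shorthand for t0. One sentence in two places would remove the doubt at almost no cost.

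Part of this stands. No shown text says in words whether intra-operative opioid is in or out, and the listed items would not allow it to be separated afterwards. The rest carries less weight. The intrathecal dose is given at time zero and has its own field, so the subgroup worry can be corrected. Epidural opioid falls in the window on both readings, so they do not disagree about it. The epidural item under Pain management serves a Yes/No rescue outcome that needs neither drug nor dose, and nothing in the protocol says these epidurals contain opioid. The sheet that sites would use, Appendix 3, is listed but not shown, so disagreement between sites is inferred without seeing their instrument.

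**Conclusion.** No change to the plan is called for. The t0 sentence is a timing rule and is compatible with a total limited to postoperative opioid, which is what the objective and the arrangement of outcomes and record items indicate. What is left is a narrow gap on intra-operative opioid, of a kind that an extraction sheet or analysis plan normally fills.

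Its size is unknown. The 10% and 33% figures are per patient, rest on assumed amounts and apply only to those given such opioid. No error in the cohort's total is shown.

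This conclusion assumes that sites follow the grouping of the items, or an extraction sheet consistent with it, and that the analysis stays descriptive. A team that wished to could state which doses count when instructing sites, but the plan does not depend on it.

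### The 6-hour answers on getting out of bed and feeding look back over surgery and block, so they are not comparable with the later answers

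*Protocol*

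**What the plan says.** Under Outcomes, the protocol sets one clock for everything: "Time intervals are specified as the time difference from the administration of the spinal anesthesia (t0"). Data collection repeats it: "Questionnaires are sent to the patient after 6, 12, 18, 24, and 48 hours, as well as 7 and 30 days after spinal anesthesia".

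The exploratory maternal outcomes include two items with a fixed look-back, each asked at 6, 12, 18, 24 and 48 hours:

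- "The impact of pain on how often the patient has gotten out of bed in the last 6 hours. 6, 12, 18, 24, 48 hours"
- "The impact of pain on how much the patient has breastfed or bottle-fed the infant in the last 6 hours"

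The answers listed for both are "4-point scale: None, a little, moderate, a lot (P"). No further answer and no separate wording for the 6-hour form is given there. The question set itself is Appendix 4, which is not shown. Data Processing and statistics plans descriptive summaries only.

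**The concern.** A 6-hour look-back asked 6 hours after the spinal injection reaches back to the injection itself. For part of that time a woman is on the operating table or still blocked, and for part of it the infant is not yet born. Asked how far pain affected getting up or feeding, she must still choose one of four levels of pain impact. Two different states can end in the same answer: she could get up and pain did not hold her back, or she could not get up and pain had nothing to do with it.

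The Objective names physical function among the things to be mapped. The other function items in the first 48 hours (independent mobilisation, nursing, personal hygiene and the Obs-QoR-10) are asked at 24 hours only, so these two items are the only repeated function measures in that period. Outcome frequencies are also meant to inform a later randomised trial, to which the outcomes were aligned. An ambiguous item could be carried forward, or a change between 6 and 12 hours could be read as a change in the effect of pain.

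**Working it through.** **Inputs.** From the protocol: t0 is the spinal injection (Outcomes); the sending times (Data collection); the 6-hour look-back and four answers (Exploratory outcomes). Not in the protocol: any expected duration of surgery or block. Operation time is collected, but no expected value is stated. The plan gives no figure on this point to reproduce.

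**Step 1: nominal windows.** Window = (sending time - 6 h) to sending time, counted from t0.

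| Sent at | Look-back |
|---|---|
| 6 h | 0-6 h |
| 12 h | 6-12 h |
| 18 h | 12-18 h |
| 24 h | 18-24 h |
| 48 h | 42-48 h |

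Only the first window starts at the injection. It must contain the operation, at least part of the block and, for feeding, time before birth.

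**Step 2: how much of the first window (assumption).** Let b be the hours after t0 in which a woman cannot get up. The share of the window is b/6:

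- b = 2: 2/6 = 33%
- b = 3: 3/6 = 50%
- b = 4: 4/6 = 67%
- b = 5: 5/6 = 83%

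This describes the window, not the bias. The answer is one ordinal judgement, not a time average. The shares are for getting up and do not carry over to feeding, which may begin before the block has worn off.

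**Step 3: late replies.** A reply d hours late shifts the window to d to 6 + d, and the overlap falls to max(0, b - d). With b = 4 and d = 2 it is 4 - 2 = 2 h, or 2/6 = 33%. Response time is an outcome ("Response time for questionnaires after 6,12,18,24,48 hours"), so the shift can be described. No answer limit is stated, and prompt replies keep the full overlap.

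**Step 4: direction (separate assumption, not implied by Step 2).** Suppose a share p = 30% had no chance to get up before answering, and pain limits 50% of the rest moderately or a lot.

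- If the 30% answer None: 0.50 x (1 - 0.30) = 35%.
- If they answer a lot: 0.50 x (1 - 0.30) + 0.30 = 65%.

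The same state can move the 6-hour figure either way.

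**Step 5: can it be undone in analysis?** The listed patient questions and medical-record fields include no time of first mobilisation or first feed. On the listed data the two states cannot be told apart afterwards.

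**The case against.** A reader might infer that the series starts artificially low and that a rise from 6 to 12 hours would appear by construction. The protocol does not support that. A blocked woman may answer None, answer a lot, or judge only the time after the block wore off. The pilot cited in the Background gives no support for a low start either: its "reported average NRS (0-10) pain scores during movement were 7" at 6 hours, then 6, 6 and 5 at 12, 18 and 24 hours. Those scores are a different measure, but they peak at the first time point. It would also be too strong to say that pain cannot limit feeding in the first window, since a leg block does not prevent feeding once the infant is born.

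Other points on the other side carry weight:

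- The items ask about the effect of pain, so None is a truthful answer from a woman kept in bed by the block. This stands. The problem is that the same answer also comes from a woman who was up and unhindered.
- Appendix 4 may already hold a not-applicable answer or different 6-hour wording, and the protocol says the questions were developed with patients and validated. This makes the fix conditional. The outcome definition still lists only four answers.
- No 6-to-12-hour comparison is planned, and presentation may be left to a SAP. This is true and limits the weight of the point. It does not supply the missing answer.
- Restricting the 6-hour percentages to women already able to get up would select early mobilisers. This is correct, so the fix keeps all responders in the denominator.

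**Conclusion.** The point holds in a limited form. By the protocol's own clock, the first look-back of both items is 0-6 h from the spinal injection, and the listed answers do not separate no limitation by pain from not yet able for another reason. The 6-hour value is not comparable with those from 12 hours onward. Direction and size are unknown; the 33% to 83% range rests on an assumed 2 to 5 h and only describes the window. The conclusion assumes prompt replies and that Appendix 4 adds no further answer.

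The weight is small: two exploratory, descriptive items. No primary or secondary outcome uses this look-back. It is a cheap improvement, not a flaw in the study's main results.

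**What to change.** 1. Check Appendix 4. If it lacks one, add to both items an answer such as: not applicable, not yet able to get up / feed for reasons other than pain. Offer it preferably at every time point, so that the response set stays the same. This also serves women who go to the ward with an epidural, which the record sheet already captures.
2. Report that answer as its own category, with all responders as the denominator.
3. Add one sentence to the analysis text: the 6-hour value covers surgery and block and is not to be read as part of the trend from 12 hours onward.

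Cost: one more category in two REDCap items and a slightly less simple 6-hour summary. No extra patient contact is needed. If the forms can no longer be changed, step 3 alone still guards against the misreading.
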